6.2. BASELINE

6.2.1. DOUBLE-BLIND BASELINE

Double-blind baseline is defined as the latest non-missing DIAN-TU-001 measurement taken prior to the double-blind study drug administration and will be consistent with the value identified as baseline during the double-blind analysis. Select imaging measures identified as failing after locking of the double-blind database a quality control during collection will be excluded from contributing to baseline.

6.2.2. OLE BASELINE

OLE Baseline is defined as the latest non-missing DIAN-TU-001 measurement taken prior to OLE study drug administration, using data from the OLE database where applicable. OLE baseline for specific assessments are as follows:

- OLE baseline for CDR Global and CDR-SB will be defined as the latest non-missing measurement prior to OLE study drug administration.
- For blood pressure, OLE baseline will further be defined as the latest time prior to OLE study drug administration where both systolic and diastolic blood pressure measurements are available.
- For laboratory assessments, OLE baseline will be defined as the values at Visit 1 of the OLE.
- OLE baseline measurements for height and weight will be derived from the values at Visit 1.

OLE Baseline will not be defined for subjects who never took the study drug. For assessments collected without a time measurement on the date of the first dose, the assessment can contribute

Author: [REDACTED]

Version Number:

7

Version Date:

07Dec2023

Template No.: CS_TP_BS016 Revision 6

Reference: CS_WI_BS005

Effective Date: 02Dec2019

to OLE baseline if it was scheduled per protocol to take place prior to dosing.

Baseline for DIAN-OBS will be defined based on the first visit in which the subject met criteria as described in [Section 5.4](#), noting that this visit will be identified at the time the subject is identified to contribute to the external controls.

6.3. RETESTS, UNSCHEDULED VISITS AND EARLY TERMINATION DATA

Summaries by visit will be based on the visit windows described in [Section 6.4](#). Early discontinuation assessments of efficacy will be included at the annual visit when it occurs +/- 6 months relative to the visit, except in cases where a scheduled visit was conducted for the corresponding annual visit. Unscheduled visits that are not captured by analysis visit windowing will not contribute to by-visit analyses.

Listings will include scheduled, unscheduled, retest and early discontinuation data.

6.4. WINDOWING CONVENTIONS

Analysis visit windows will be applied based on the planned frequency of collection outlined in the protocol. Planned visit dates will be calculated from the date of the first OLE dose at V1 (Week 0). For data collected yearly, visit windows will begin 182 days prior to the planned visit date and end 182 days after the planned visit date. For data collected semi-annually, visit windows will begin 91 days prior to the planned visit date and end 91 days after the planned visit date. Safety/titration MRI's and measurements collected more frequently than a semi-annual basis (e.g., vital signs) will be summarized based on the nominal visit. If multiple measurements fall within the same visit window, the value closest to the planned visit timepoint per the protocol schedule of events will contribute to by-visit summaries, with the later visit to be used

Author: [REDACTED]

Version Number:

7

Version Date:

07Dec2023

Template No.: CS_TP_BS016 Revision 6

Reference: CS_WI_BS005

Effective Date: 02Dec2019

in the case of a tie.

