The MRI schedule may be changed according to the ARIA-related dosing intervention algorithm (see tables in Section 1.14) or per individual request by the site principal investigator or delegated sub-investigator, Project Arm Leader (PAL), or Medical Director or designee.

Refer to prior amendments for details regarding the MRI schedule relative to dosing in the double-blind period.

For the OLE Period, all participants will have Safety MRIs performed (Figure 1) at the following time points:

- Titration Period: prior to each up-titration

- Once at the target dose of [REDACTED] (or highest dose a participant reaches in case of safety issues): approximately every [REDACTED] doses (approximately every [REDACTED] weeks) for the first year at that dose; refer to schedule of events for exact timing.
- The first annual OLE visit will occur at Week 48 after the third dose of [REDACTED] to obtain the annual/safety MRI prior to subsequent up-titration. In cases where approval and consenting to Amendment 11 does not occur prior to a participant reaching Week 48, initiation of up-titration should occur once consent has been signed and per approved titration and MRI schedule once reviewed by the medical monitoring team.

The first 20 participants to dose at each of the two additional titration steps beyond [REDACTED] [REDACTED] will have an additional safety MRI after the first two [REDACTED] doses (sentinel safety cohort) at each titration step as follows:

- [REDACTED]
i [REDACTED]

The DIAN-TU Medical Monitors will perform a safety review of the sentinel cohort data to ensure no issues or concerns are detected, and ensure there are no findings that would warrant additional scanning of additional participants.

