- Vital signs (blood pressure, heart rate, respiratory rate, and body temperature; weight may be obtained approximately every 3 months per Section 6.1.6 of the main protocol)
- Blood collection for the following:
 - CCI
[REDACTED]
 - Stored plasma
- C-SSRS administration
- Urine pregnancy testing for POBCP
- Drug product dosing and post-dose monitoring/evaluation as specified in Section 2.5
- Phone call (not required at all home/off-site visits but direct site-participant contact should occur at least once every 3 months throughout the study): the DIAN-TU site coordinator calls participant and addresses any concerns, discusses scheduling of safety MRI and next visits, and encourages compliance.

3.2.5 OLE VISITS 13, 27, and 40 or Early Termination: ANNUAL VISIT AT DIAN-TU SITE

Location: DIAN-TU site

Timing: 48 and 104, and 156 weeks \pm 7 days (or Early Termination) from day of first dose at OLE Visit 1; approximately a 2- to 3-day visit. The second dose administration for Q2W dosing associated with each visit should be completed at weeks 50, 106, and 158 weeks \pm 3 days, respectively, and will include vitals, concomitant medications, and AEs as outlined in the Schedule of Visits. The sequence and timing of visit procedures is very important.

Requirements and suggested timing of study procedures are detailed in the *Global Manual of Operations*. For participants who live near the study site, these visit procedures may be scheduled over a longer time period of up to 2 weeks.

Procedures:

- Concomitant Medications
- Adverse Event Assessment
- Vital signs (blood pressure, heart rate, respiratory rate, and body temperature); weight and height
- Administration of C-SSRS

- Blood collection for the following:
 - Clinical laboratory tests (hematology, chemistry, urinalysis)
 - CCI [REDACTED]
- Urine pregnancy testing for POCBP
- Physical and neurological examination
- Clinical assessments:
 - Clinical Dementia Rating (CDR) including calculation of Clinical Dementia Rating Sum of Boxes (CDR-SB)
 - Assessment of clinical diagnosis and clinician judgment of symptoms
 - CCI [REDACTED]

OTE: For each participant, the CDR and assessment of clinical diagnosis should be administered by the same experienced clinician at all visits. Whenever possible the CDR rater should not be involved in other clinical assessments (e.g., MMSE, FAS, GDS, NPI-Q) or in cognitive testing.

- Complete Cognitive Battery (see Section 3.2)
- CCI [REDACTED]

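### The fixed ±182 and ±91 day windows in SAP 6.4 do not fit the uneven OLE visit schedule, so an off-schedule value can fall in no visit window or in two

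*SAP*

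**What the plan says.** SAP 6.4 counts planned dates from the first OLE dose (week 0). Its rule for annual measures is that "visit windows will begin 182 days prior to the planned visit date and end 182 days after the planned visit date". Semi-annual measures get the same construction with 91 days on each side. If several values share a window, "the value closest to the planned visit timepoint per the protocol schedule of events will contribute to by-visit summaries", and the later value wins a tie. No rule covers one value that lies in two windows.

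The schedule that 6.4 points to is in Protocol Appendix 3:
- Section 3.2.5 puts the annual visits at "48 and 104, and 156 weeks", ±7 days. Section 1.13.1 agrees: "The first annual OLE visit will occur at Week 48 after the third dose of" a redacted dose level.
- Sections 3.2.4 and 3.2.6 put the mid-year visits at week 24 (±4 days) and at weeks 76 and 128 (±3 days).

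SAP Appendix 1 (Presentation of Visits) labels Year 1 as week 48/52 at Visit 14, because an amendment moved it. The protocol's first annual visit is Visit 13. SAP 6.4 does not say which week anchors the Year 1 window.

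SAP 6.3 places early-discontinuation efficacy data at an annual visit if they fall within six months of it, unless the scheduled visit was done. It adds: "Unscheduled visits that are not captured by analysis visit windowing will not contribute to by-visit analyses".

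**The concern.** The primary PiB-PET model (SAP 16.1.3) and the MMRMs for CSF pTau181 and CSF Aβ42/40 (16.2.3.4, 16.2.3.5) treat visit as a category. Each value therefore needs exactly one visit. A value in no window has no visit to enter under, and a value in two windows can enter twice.

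Analysis windows exist to place off-schedule data, and the documents make such data plausible:
- The SAP change log records that the OLE was terminated early.
- Protocol Appendix 3, section 2.2 accepts that participants who start the later titration steps late may not line up with the schedule's week numbers.
- Protocol Appendix 3, section 3.2.8 lets PET be omitted at early termination if the last PET was less than six months before. After an on-time Year 1 scan at day 336, that exemption ends at about day 336 + 183 = 519, which is where the annual gap opens.

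**Working it through.** **Inputs.** Half-widths of 182 and 91 days (SAP 6.4). Planned weeks 24, 48, 76, 104, 128 and 156 (Protocol Appendix 3, sections 3.2.4 to 3.2.6). Alternative Year 1 week 52 (SAP Appendix 1). PiB-PET at baseline and annually in the OLE (main protocol 6.1.18; the PET rows of the OLE schedule are redacted). Days are counted from first dose as day 0.

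**Origin of the half-widths.** 52 × 7 / 2 = 182 and 26 × 7 / 2 = 91. They are exact for even spacing. The protocol's annual intervals are 48, 56 and 52 weeks, and its semi-annual intervals are 24, 24, 28, 28, 24 and 28 weeks.

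**Window = 7 × planned week ± half-width.**

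| Data | Year 1 anchor | Windows (days) | Gaps | In two windows |
|---|---|---|---|---|
| Annual | week 48 | 154-518, 546-910, 910-1274 | 519-545 (27 days) | 910 |
| Annual | week 52 | 182-546, 546-910, 910-1274 | none | 546, 910 |
| Semi-annual | week 48 | 77-259, 245-427, 441-623, 637-819, 805-987, 1001-1183 | 428-440, 624-636, 988-1000 (13 days each) | 245-259, 805-819 (15 days each) |
| Semi-annual | week 52 | 77-259, 273-455, 441-623, 637-819, 805-987, 1001-1183 | 260-272, 624-636, 988-1000 (13 days each) | 441-455, 805-819 (15 days each) |

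**Who is affected.** With week 48, a scan in the annual gap is 519 − 336 = 183 to 545 − 336 = 209 days late for Year 1. It is equally 728 − 545 = 183 to 728 − 519 = 209 days early for Year 2. Every day within the protocol's own tolerances (±3, ±4 or ±7 days) falls in exactly one window.

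**Does SAP 6.3 close the gap?** Taking six months as 183 days (an assumption), the Year 1 reach ends at 336 + 183 = 519 and the Year 2 reach starts at 728 − 183 = 545. Days 520-544 (25 days) stay uncovered.

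**Midpoint cuts.**
- Week 48, annual: (336 + 728)/2 = 532 and (728 + 1092)/2 = 910.
- Week 48, semi-annual: (168 + 336)/2 = 252, (336 + 532)/2 = 434, (532 + 728)/2 = 630, (728 + 896)/2 = 812 and (896 + 1092)/2 = 994.
- Week 52 changes only the cuts next to Year 1: annual (364 + 728)/2 = 546; semi-annual (168 + 364)/2 = 266 and (364 + 532)/2 = 448.

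**The case against.** A reader might infer that primary PiB scans have been lost and that mid-year scores have been counted twice. The documents do not support that, for these reasons:
- **The annual gap depends on the anchor.** It disappears with week 52, and the SAP does not fix the anchor.
- **On-schedule visits are safe.** Only values about six months off an annual visit, or well off a mid-year visit, are exposed, and no count of them is given. The change log reports missing PET scans, not late ones.
- **Discarded is not stated.** The exclusion in SAP 6.3 names unscheduled visits only. For a scheduled but very late scan the SAP is silent. Such a scan would still be listed, and could serve as the last post-baseline value in the shift analysis (16.1.4.4).
- **The primary conclusion is drawn at Year 3.** The Year 2/Year 3 boundary has no gap, only shared day 910.
- **Double use is narrow.** A value in an overlap counts twice only if neither window holds a value nearer its own planned date. The LME models use continuous time (16.2.3.3) and the CDR analyses use time to event. The cognitive composite is not computed at mid-year visits, because the subset battery omits category fluency (Protocol Appendix 3, section 3.2; SAP 16.2.2).

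All of this stands, and it limits the size of the problem. It does not remove it: neither anchor assigns every day to exactly one visit, and no rule settles the days left over.

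**Conclusion.** The point holds as a minor defect in the windowing rule. With Year 1 at week 48, an off-schedule or early-termination annual measurement, PiB-PET included, on days 519-545 has no window. With week 52 that gap closes, but days 546 and 910 are shared. Semi-annual gaps and overlaps exist under either anchor.

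The Year 1 and Year 2 PiB estimates could be affected directly. Apart from a scan on day 910 itself, the Year 3 test is affected only indirectly, through the Year 1 and Year 2 data in the repeated-measures model. The semi-annual faults mainly concern by-visit summaries such as MMSE.

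This rests on reading the windows as inclusive at both ends, and on PiB-PET being done at the annual visits. The number of affected values is unknown and may be zero.

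**What to change.** 1. State in SAP 6.4 whether week 48 or week 52 anchors Year 1, and reconcile the visit label in SAP Appendix 1 with the protocol.
2. Replace the fixed half-widths with contiguous windows cut midway between planned visits, each boundary day assigned to one visit. With week 48, cut annual data at days 532 and 910, and semi-annual data at days 252, 434, 630, 812 and 994. With week 52, use 546 in place of 532, and 266 and 448 in place of 252 and 434. These are days after first dose; add 1 for Study Day as SAP 6.1 defines it.
3. Apply the same windows to early-termination assessments in SAP 6.3, in place of the six-month rule.

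No data are lost. The cost is a small SAP change made late: version 7 already postdates the interim and the early termination, and the results are open-label. It should be documented and justified before database lock, with a list of any values whose visit assignment changes.

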6.5. STATISTICAL TESTS

The default significant level will be (5%); confidence intervals will be 95% and all tests will be two-sided, unless otherwise specified in the description of the analyses.

6.6. COMMON CALCULATIONS

Scores for CDR Global and CDR-SB will be reported based on the value entered in the database and will not be recalculated.

For quantitative measurements, change from baseline will be calculated as post-baseline assessment - baseline assessment. If either the baseline or post-baseline value is missing, the observation will not be included in the change from baseline summary.

EYO equals a subject's age at the clinical assessment minus this subject's estimated age at onset (AO). The details of the estimated AO are provided in the double-blind period SAP, Section 12.1.2, noting that Appendix III of this SAP will be used for analysis rather than the Appendix II in the double-blind SAP. CRF visit date will be used for the calculation of EYO to ensure a constant value across all tests within a visit.

6.7. SOFTWARE VERSION

All analyses, summary tables, figures, and data listings will be generated with SAS® version 9.4 or higher, or R, or with analysis code that has been appropriately validated.

7. STATISTICAL CONSIDERATIONS

[REDACTED] [REDACTED]

Author: [REDACTED]

Version Number: 7

Version Date: 07Dec2023

Template No.: CS_TP_BS016 Revision 6

Reference: CS_WI_BS005

Effective Date: 02Dec2019

7.1. ADJUSTMENTS FOR COVARIATES AND FACTORS TO BE INCLUDED IN ANALYSES

The following covariates and factors are used in the analyses. For details of their inclusion in the models, see the specific analysis section.

- Double-blind baseline CDR Global
 - CDR=0 (asymptomatic)
 - CDR>0 (symptomatic)
- OLE baseline CDR Global
 - CDR=0 (asymptomatic)
 - CDR>0 (symptomatic)
- Double-blind baseline PiB-PET SUVR
 - PiB-PET SUVR ≤ 1.25
 - PiB-PET SUVR > 1.25
- OLE baseline PiB-PET SUVR
 - PiB-PET SUVR ≤ 1.25
 - PiB-PET SUVR > 1.25
- Time since OLE baseline (in years; continuous)
- Time since double-blind baseline (in years; continuous)
- Double-blind baseline EYO (in years; continuous)
- OLE baseline EYO (in years; continuous)
- Post-baseline EYO (in years; continuous)

For external controls, baseline values will be identified as the last measurement at or prior to the first visit for the subject to be identified as contributing to the external controls.

Author: [REDACTED]

Version Number:

7

Version Date:

07Dec2023

Template No.: CS_TP_BS016 Revision 6

Reference: CS_WI_BS005

Effective Date: 02Dec2019

7.2. MULTICENTER STUDIES

This platform study is conducted in three regions, USA/Australia/Canada, Europe, and the rest of the world. This study is being conducted at approximately 30 global sites. The homogeneity of treatment effects across investigational sites will be investigated using descriptive statistics.

When specified, statistical analysis will be adjusted for geographic region. Geographic region will be categorized as follows:

Geographic Region	Country
United States/Canada/Australia	United States, Canada and Australia
Europe	France, Spain, United Kingdom, as well as any European countries available from external controls.
Rest of World	The rest of world besides the above 2 regions, based on countries applicable to external controls.

7.3. MISSING DATA

There will be no imputation of missing data. Handling of missing data for specific efficacy endpoints is detailed in [Sections 16.1.2](#) and [16.2.2](#).

7.4. MULTIPLE COMPARISONS/ MULTIPLICITY

There will be no adjustments for multiplicity or multiple comparisons for the open label analysis as the study was powered based on the double-blind analysis.

Author: [REDACTED]

Version Number:

7

Version Date:

07Dec2023

Template No.: CS_TP_BS016 Revision 6

Reference: CS_WI_BS005

Effective Date: 02Dec2019

7.5. EXAMINATION OF SUBGROUPS

Subgroup analysis will be conducted as described within [Section 16](#) for the primary variables, (key) secondary variables, and exploratory variables.

8. OUTPUT PRESENTATIONS

Appendix 1 shows conventions for presentation of data in outputs.

The templates provided with this SAP describe the presentations for this study and therefore the format and content of the summary tables, figures, and listings to be provided by [REDACTED]
[REDACTED]

9. DISPOSITION AND WITHDRAWALS

All mutation positive subjects who provide informed consent for the Gantenerumab OLE will be accounted for in this study period.

9.1. DISPOSITION

Subject disposition and withdrawals and study region will be presented for the ENR set, and presented separately by baseline asymptomatic and symptomatic status for the OLE Gant mITT population. In addition, visit attendance will be listed and summarized for each scheduled visit. Reasons for end of study and end of treatment will be presented in a listing. An additional listing will include subjects who did not meet one or more eligibility criteria.

Summaries for disposition will be presented for the interim analysis and will also identify the number of subjects who are active in the study as of the interim analysis datacut.

Author: [REDACTED]

Version Number:

7

Version Date:

07Dec2023

Template No.: CS_TP_BS016 Revision 6

Reference: CS_WI_BS005

Effective Date: 02Dec2019

9.2. PROTOCOL DEVIATIONS

A summary will be provided to identify subjects who had important protocol violation(s) and a list will be provided for important protocol violation(s). The identification of the important protocol violation(s) will be discussed at the data review meeting prior to final database lock.

10. DEMOGRAPHIC AND OTHER BASELINE CHARACTERISTICS

Demographic data and other baseline characteristics will be presented for each mITT population (along with their associated controls) and the SAF. No statistical testing will be carried out for demographic or other baseline characteristics. The univariate summary statistics, n, mean (SD), median, minimum and maximum will be calculated for the continuous variables. The following demographic and other baseline characteristics will be reported, where values will be presented as collected prior to double-blind treatment if the value was not collected in the open label database:

- Age (years) - calculated relative to date of consent for the OLE, based on date of birth as collected in the double-blind period
- Sex
- Race (where subjects can contribute to multiple race categories)
- Ethnicity
- OLE Baseline CDR Global
- OLE Baseline CDR-SB (summarized both as a continuous value and an ordinal value)
- OLE Baseline EYO
- Years of Education

[REDACTED] [REDACTED]

Author: [REDACTED]

Version Number:

7

Version Date:

07Dec2023

Template No.: CS_TP_BS016 Revision 6

Reference: CS_WI_BS005

Effective Date: 02Dec2019

- OLE Baseline Height
- OLE Baseline Weight

For the OLE Gant All Gant exposure mITT and All Gant exposure mITT populations, values for the double-blind period baseline for age, CDR Global, CDR-SB, EYO, height and weight will also be presented for subjects in the population who were randomized to gantenerumab during the double-blind period.

Demographic data will also be presented in a listing.

Demographic data will be summarized for the interim analysis for each mITT population and associated controls.

11. MEDICAL HISTORY

Updated Medical History information collected in the OLE eCRF will be listed for the SAF, and select family history as collected prior to the double-blind period will be summarized

- Medical History will be coded using Medical Dictionary for Regulatory Activities (MedDRA) System Organ Class (SOC) and Preferred Term (PT). The version will be established and documented prior to lock of the data and will be identified within footnotes.
- Family AD History as indicated by symptoms, history or diagnosis will be summarized by descriptive statistics and listed for the OLE Gant mITT and the SAF. Mutation gene types (PSEN1, PSEN2, and APP), APOE4 status (as positive/negative, as number of copies (0, 1, or 2), and by allele combinations), number and percentage of blood grandparents and parents, siblings, and children in a family with dementia will also be tabulated.

Author: [REDACTED]

Version Number:

7

Version Date:

07Dec2023

Template No.: CS_TP_BS016 Revision 6

Reference: CS_WI_BS005

Effective Date: 02Dec2019

12. COLUMBIA – SUICIDE SEVERITY RATING SCALE (C-SSRS)

The OLE baseline C-SSRS score, as obtained using the Since Last Visit version of the form, will be summarized using descriptive statistics by severity rating scale for each category of Suicidal Ideation, Intensity of Ideation, and Suicidal Behavior for the SAF. C-SSRS scores will also be listed.

